**PAGE 57/103** 

The two hypothesis tests are hierarchically structured so that the second test (superiority) will only be considered if the first test (non-inferiority) is rejected. The superiority test is powered to detect an absolute difference of 18%. There is no alpha adjustment for the second test as a result of the hierarchical testing.

# **10.3** Significance Testing and Estimations

The primary endpoint of treatment success will be tested sequentially with the first test being non-inferiority test based upon the treatment difference.

A two-sided 95% CI for the difference of the two clinical success rates (Eziclen®/Izinova® minus Klean-Prep®) will be calculated. If and only if the lower limit of the CI is greater than the lower limit of equivalence region -15%, Eziclen®/Izinova® is proven to be not less effective than Klean-Prep®.

A rejection of the null hypothesis will trigger superiority testing based upon treatment difference. If the lower limit of the CI is greater than zero, Eziclen®/Izinova® is proven to be superior to Klean-Prep®.

#### 10.4 Statistical/Analytical Methods

Statistical analyses will be performed by an external CRO, managed by the sponsor's Biometry Department.

A statistical and analysis plan (SAP) describing the planned statistical analysis in detail with tables, figures and listings templates will be developed as a separate document.

Statistical evaluation will be performed using Statistical Analysis System (SAS)® (version 9.2 or higher).

#### 10.4.1 Demographic and Other Baseline Characteristics

In order to ensure balance of treatment groups, descriptive summary statistics (n, mean, standard deviation (SD), median, minimum, maximum) or frequency counts of demographic and baseline data (medical history, prior medications and prior non-drug therapy, etc.) will be presented by treatment group and overall for the ITT, mITT and PP populations if they differ by more than 10%.

# 10.4.2 Homogeneity of Treatment Groups

In order to assess the homogeneity of treatment groups at Baseline, descriptive statistics and other baseline characteristics will be tabulated for each treatment group along with 95% CI.

#### 10.4.3 Subject Disposition and Withdrawals

The numbers and percentages of subjects enrolled and included in each of the ITT, mITT, PP and safety populations will be tabulated by country and centre. The reasons for subject exclusions from each of the populations will also be tabulated. In addition, the numbers of subjects who were randomised, discontinued and completed at each of the study periods (e.g. active follow-up) will be tabulated by treatment group. Primary reasons for discontinuation of study treatment will be tabulated.

# 10.4.4 Pharmacokinetic Data

Not applicable.

PAGE 58/103

#### 10.4.5 Efficacy Evaluation

As indicated in Section 7.1, the primary efficacy variable is the proportion of subjects with successful overall preparation evaluated with the scale (from 1 to 4) of the Cleansing Score as assessed by the colonoscopist.

A successful preparation will be defined as excellent (4) or good (3) preparation.

A failure preparation will be defined as:

- Fair (2) or poor (1) according to bowel cleansing
- Any subject who did not have a colonoscopy based on the investigator's assessment of the cleansing (insufficient faecal output, unclear faecal discharge, etc.) or due to preparation related AEs.
- Any subject for whom cleaning was not adequate for evaluation.
- Any subject for whom rescue treatment (saline enema) was needed.

The proportion of subjects with successful colon cleansing (graded as excellent or good) will be summarised along with the 95% confidence interval (CI) using the standard Wald asymptotic CI. The primary efficacy endpoint will be analysed using a logistics regression model including country as stratified variable, the interaction between country and treatment will be also investigated. The formal hypothesis test result (p-value) for treatment difference will be presented together with a two-sided 95% CI for the difference in success rates. The non-inferiority will be demonstrated if the lower limit of the 95% CI of that difference is higher than -15%.

If the non-inferiority is demonstrated, the superiority will be analysed based upon treatment difference. If the lower limit of the CI is greater than zero, Eziclen®/Izinova® is proven to be superior to the Klean-Prep®.

Secondary efficacy endpoints are presented in Section 7.2.

Results will be tabulated by treatment group and overall using descriptive summary statistics (mean SD, median, interquartiles and ranges) or frequency count with two-sided 95% CI when appropriate.

Time to clear effluent data will be analysed by using survival methods. The results will be presented both in summary tables (number of events, censors, median and interquartile time to event with 95% CI...) and graphically in Kaplan-Meier plots by treatment group and overall. This will be detailed in the SAP.

Other secondary endpoints will be analysed using Cochran-Mantel-Hænszel (CMH) chi-square for count (percentage) adjusting for country effect and two-way analysis of variance (ANOVA) for continuous parameters including treatment, country and their interaction as covariates.

# 10.4.6 Adjustment for Country/Centre Effect

An adjustment for country effect will be planned for the analysis of primary efficacy by country as covariates.

Descriptive analysis by country will be carried out.

#### 10.4.7 Safety Evaluation

All safety data will be included in the subject data listings. Analyses and summary tables will be based upon the safety population.

**PAGE 59/103** 

All AEs will be coded according to the MedDRA and will be classified by MedDRA preferred term and system organ class. AE listings will be presented by subject, system organ class and preferred term.

Incidence of all reported TEAE and SAEs will be tabulated by treatment group and overall. In addition, summary tables will be presented by maximum intensity, drug relationship and AEs/TEAEs associated with premature withdrawal of study medication.

A TEAE is defined as any AE that occurs during the active phase of the study if:

- It was not present prior to receiving the first dose of IMP, or
- It was present prior to receiving the first dose of IMP but the intensity increased during the active phase of the study.

All TEAEs will be flagged in the AEs listings.

Concomitant medication will be coded by using World Health Organisation (WHO) Drug Dictionary and will be summarised by treatment group and overall with the number and percentage of subjects receiving concomitant medication by drug class and preferred drug name.

Summary statistics (mean, median, SD and range as appropriate) by treatment group and overall will be presented for vital signs, BP, HR, clinical laboratory tests (blood and urine sample), physical examination, etc. at each assessment with change from Baseline. For laboratory data, abnormal values will be flagged in the data listings and a list of clinically significant abnormal values will be presented. Shift tables will be presented of the number and percentage of subjects with low, normal or high values and normal or abnormal exams.

Frequency count with two-sided 95%CI when appropriate by treatment group and by overall will be presented for symptom questionnaire data (stomach cramping, stomach bloating and nausea) on a 5-point scale (see Table 11).

# 10.5 Subgroup Analyses

Descriptive statistics for primary endpoint may be provided per country.

# 10.6 Interim Analyses

No interim analysis will be performed.

An Expert Committee chaired by the principal investigator will review safety data. This review will be performed during blind data review meetings. Full details of the operating model for this safety data review will be provided in a charter to be produced.

PAGE 60/103

#### 11 DIRECT ACCESS TO SOURCE DATA AND DOCUMENTS

Authorised personnel from external CAs and sponsor authorised Quality Assurance personnel may carry out inspections and audits. The purpose of an audit is to ensure that ethical, regulatory and quality requirements are fulfilled in all studies performed by the sponsor.

Auditors and inspectors must have direct access to study documents and site facilities as specified in Section 12.4 and to any other locations used for the purpose of the study in question (e.g. laboratories).

In the event of the site being notified directly of a regulatory inspection, the investigator must notify the sponsor's representative as soon as possible, to assist with preparations for the inspection.

PAGE 61/103

# 12 QUALITY CONTROL AND QUALITY ASSURANCE

#### 12.1 Protocol Amendments and Protocol Deviations and Violations

#### 12.1.1 Protocol Amendments

No changes from the final approved (signed) protocol will be initiated without the prior written approval or favourable opinion of a written amendment by the IEC/IRB, except when necessary to eliminate immediate safety concerns to the subjects or when the change involves only logistics or administration. The principal investigator and the sponsor will sign the protocol amendment.

# 12.1.2 Protocol Deviations, Violations and Exceptions

A protocol deviation is nonadherence to protocol specific study procedures or schedules that does not involve inclusion/exclusion criteria, primary objective evaluation criteria, and/or GCP guidelines. Deviations are considered minor and do not impact the study.

A protocol violation is any significant divergence from the protocol, i.e. nonadherence on the part of the subject, the investigator, or the sponsor to protocol specific inclusion/exclusion criteria, primary objective evaluation criteria and/or GCP guidelines. Protocol violations will be identified and recorded, by study centre personnel, on the eCRF.

As a matter of policy, the sponsor will not grant exceptions to protocol specific entry criteria to allow subjects to enter a study. If under extraordinary circumstances such action is considered ethically, medically and scientifically justified for a particular subject, prior approval from the sponsor and the responsible IRB/IEC, in accordance with the Standard Operating Procedure (SOP), is required before the subject will be allowed to enter the study. If investigative centre personnel learn that a subject who did not meet protocol eligibility criteria was entered in a study (a protocol violation), they must immediately inform the sponsor. Such subjects will be discontinued from the study, except in an exceptional instance following review and written approval by the sponsor and the responsible IRB/IEC, according to the applicable SOP.

# 12.2 Information to Study Personnel

The investigator is responsible for giving information about the study to all staff members involved in the study or in any element of subject management, both before starting any study procedures and during the course of the study (e.g. when new staff become involved). The investigator must assure that all study staff members are qualified by education, experience and training to perform their specific responsibilities. These study staff members must be listed on the study centre authorisation form, which includes a clear description of each staff member's responsibilities. This list must be updated throughout the study, as necessary.

The study monitor is responsible for explaining the protocol to all study staff, including the investigator and for ensuring their compliance with the protocol. Additional information will be made available during the study when new staff become involved in the study and as otherwise agreed upon with either the investigator or the study monitor.

# 12.3 Study Monitoring

The investigator is responsible for the validity of all data collected at the site.

The sponsor is responsible for monitoring this data to verify that the rights and wellbeing of subjects are protected, that study data are accurate (complete and verifiable to source data) and that the study is conducted in compliance with the protocol, GCP and regulatory requirements. Sponsor assigned monitors will conduct regular site visits. The investigator will allow direct access to all relevant files (for all subjects) and clinical study supplies (dispensing and storage

PAGE 62/103

areas) for the purpose of verifying entries made in the eCRF, and assist with the monitor's activities, if requested. Adequate time and space for monitoring visits should be made available by the investigator.

The site must complete the eCRFs according to the sponsor monitoring manual, of the subject's visit and on an ongoing basis to allow regular review by the study monitor, both remotely by the internet and during site visits. The central study monitor at the sponsor will use functions of the electronic data capture (EDC) system to address any queries raised while reviewing the data entered by the study site personnel in a timely manner.

Whenever a subject name is revealed on a document required by the sponsor (e.g. laboratory print outs) the name must be blacked out permanently by the site personnel, leaving the initials visible and annotated with the subject number as identification.

# 12.4 Audit and Inspection

Authorised personnel from external CAs and the sponsor's authorised Quality Assurance personnel may carry out inspections and audits (see Section 11).

# 12.5 Data Quality Assurance

Monitored eCRFs transferred from the investigational site to the assigned Data Management group will be reviewed (secondary monitoring) for completeness, consistency, legibility and protocol compliance.

Reasons should be given on the relevant eCRF for any missing data and other protocol deviations. Any electronic queries and items not adequately explained will require additional electronic manual queries to be raised to the investigator by the monitor for clarification/correction. The investigator must ensure that queries are dealt with promptly. All data changes and clarifications can be viewed in the audit trail function of the eCRF.

PAGE 63/103

#### 13 ETHICS

# 13.1 Compliance with Good Clinical Practice and Ethical Considerations

This study will be conducted in compliance with IECs/IRBs, informed consent regulations, the Declaration of Helsinki and ICH GCP Guidelines (Section 1.6).

The FDA, 21 CFR Part 11, Electronic Records, Electronic Signatures and FDA, Guidance for Industry: Computerised Systems Used in Clinical Trials are a regulations which provides criteria for acceptance by the FDA, under certain circumstances, of electronic records, esignatures and hand-written signatures executed to electronic records as equivalent to paper records and hand-written signatures on paper.

In addition, this study will adhere to all local regulatory requirements.

Before initiating a study, the investigator/institution should have written and dated approval/favourable opinion from the IEC/IRB for the study protocol/amendment(s), written ICF, assent form, any consent or assent form updates, subject emergency study contact cards, subject recruitment procedures (e.g. advertisements), any written information to be provided to subjects and a statement from the IEC/IRB that they comply with GCP requirements. The IEC/IRB approval must identify the protocol version as well as the documents reviewed.

After IEC/IRB approval, changes will require a formal amendment. Once the study has started, amendments should be made only in exceptional circumstances. Changes that do not affect subject safety or data integrity are classified as administrative changes and generally do not require ethical approval. If ethically relevant aspects are concerned, the IEC/IRB must be informed and, if necessary, approval sought prior to implementation. Ethical approval on administrative changes will be obtained if required by local/site IEC/IRB.

#### 13.2 Informed Consent and Assent

Prior to study entry, the investigator, or a person designated by the investigator, will explain the nature, purpose, benefits and risks of participation in the study to each subject, subject's legally acceptable representative or impartial witness. Written informed consent must be obtained prior to the subject entering the study (before initiation of any study-related procedure and administration of the IMP) from the subject's parent(s)/legal representative and an assent from the subject. Sufficient time will be allowed to discuss any questions raised by the subject and subject's parent(s)/legal representative.

The sponsor will provide a sample ICF and a sample assent. The both final versions controlled forms must be agreed to by the sponsor and the IEC/IRB and must contain all elements included in the sample forms, in language readily understood by the subject and parent(s)/legal representative. Each subject's original consent form and assent form, personally signed and dated by the subject and by the subject's legally acceptable representative, and by the person who conducted the informed consent discussion, will be retained by the investigator. The investigator will supply subjects and parent(s)/legal representative with a copy of their signed informed consent.

The consent form may need to be revised during the study should important new information become available that may be relevant to the safety of the subject or as a result of protocol amendments. In this instance, approval should always be given by the IEC/IRB. It is the investigator's responsibility to ensure that all subjects subsequently entered into the study and those currently in the study sign the amended form. This is documented in the same way as previously described. Subjects who have completed the study should be informed of any new information that may impact on their welfare/wellbeing.

**PAGE 64/103** 

The investigator should, with the consent of the subject, inform the subject's primary physician about their participation in the clinical study.

# 13.3 Health Authorities and Independent Ethics Committees/Institutional Review Boards

As required by local regulations, the sponsor's Regulatory Affairs group will ensure all legal regulatory aspects are covered and obtain approval of the appropriate regulatory bodies, prior to study initiation in regions where an approval is required.

# 13.4 Confidentiality Regarding Study Subjects

The investigator must assure that the privacy of the subjects, including their personal identity and all personal medical information, will be maintained at all times. In CRFs and other documents or image material submitted to the sponsor, subjects will be identified not by their names, but by an identification code (e.g. initials and identification number).

Personal medical information may be reviewed for the purpose of verifying data recorded on the CRF. This review may be conducted by the study monitor, properly authorised persons on behalf of the sponsor, the quality assurance unit, or regulatory authorities. Personal medical information will always be treated as confidential.

PAGE 65/103

#### 14 DATA HANDLING AND RECORD KEEPING

# 14.1 Data Recording of Study Data

In compliance with GCP, the medical records/medical notes, etc, should be clearly marked and permit easy identification of a subject's participation in the specified clinical study.

The investigator must record all data relating to protocol procedures, laboratory data, safety data and efficacy ratings on the eCRFs provided for the study. The investigator, by completing the signature log, may formally designate authority to complete eCRFs to appropriately qualified staff having certified user access to the eCRF. Subject/caregiver completed questionnaires will be printed.

The unblinded personnel must record all the data relating to IMP administration and subject's leaflet questionnaire.

The investigator must, as a minimum, provide an electronic signature (e-signature) to each case report book to attest to the accuracy and completeness of all the data. If any changes are made to the eCRF, after a form has been locked and electronically signed, the investigator will be required to perform an additional e-signature authorising agreement with any new information or changes to the eCRF.

All corrections on the eCRF will be automatically tracked and a reason for change is always required. In the eCRF, the audit trail function will allow the changes made to be viewed on each item entered.

# 14.2 Data Management

#### 14.2.1 eCRF

Electronic Data Capture (EDC) will be utilised for collecting subject data. Each site is required to have a computer and internet connection available for site entry of clinical data. All entries in the eCRF will be done under the electronic signature of the person performing the action. This electronic signature consists of an individual and confidential username and password combination. It is declared to be the legally binding equivalent of the handwritten signature. Only sponsor authorised users will have access to the eCRF as appropriate to their study responsibilities. Users must have successfully undergone software application training prior to entering data into the eCRF.

Data management will be conducted by a CRO, directed by the sponsor's data management department. All data management procedures will be completed in accordance with the sponsor and the contracted CRO SOPs. Prior to data being received in-house at the assigned CRO, it will be monitored at the investigator site, (for further details please see Section 12.3 Monitoring Procedures). The eCRF and other data documentation removed from the investigator site(s) will be tracked by the CRO and the monitor.

The sponsor will ensure that an appropriate eCRF is developed to capture the data accurately, and suitable queries are raised to resolve any missing or inconsistent data. The investigator will receive their data, from the clinical study, in an electronic format (PDF files) which will be an exact copy of the eCRF, and will include the full audit trail, for archiving purposes and future reference.

Any queries generated during the data management process will also be tracked by the contracted data management CRO/will be raised within the EDC system. It is the central study monitor's responsibility to ensure that all queries are resolved by the relevant parties.

**PAGE 66/103** 

The sponsor will also ensure that SAE data collected in the eCRF are consistent with information provided to the sponsor's pharmacovigilance department (and vice versa).

The coding of an AE, medical history and any medical terms (e.g. concomitant non-drug therapy, concomitant surgeries) will be performed by the CRO, directed by the sponsor's Biometry Group, and reviewed and approved by the sponsor. Concomitant medications will be coded using WHODRUG and AEs/medical history terms will be coded using MedDRA.

Each subject will be identified with a unique subject identification number. All study documents related to a subject will be identified with this subject number.

Subject's leaflet where all information with regards to treatment Administration questionnaire, Information about subject's bowel movement, Treatment Acceptability Questionnaire and Symptoms Scale completed by the subject/caregiver will be single-entered by unblinded personnel at the Investigational site in the eCRF put in place by the sponsor. The principal investigator will ensure that these data are complete and accurately represent the study subject information by electronically signing the e-CRF.

Subject's leaflet where all information with regards to treatment administration questionnaire will be used to enter some (summary) data in e-CRF by the authorised staff at the investigational site in the e-CRF.

# 14.2.2 Subject/Caregiver Leaflet/Questionnaires

After randomisation at Visit 1 the subject will be provided with:

- Either the Eziclen®/Izinova® leaflet
- Or the Klean-Prep® leaflet

The subject's leaflet will be printed on single copy paper and provided to the principal investigator/study nurse who will file it in the subject's medical/study file

The leaflet will contain:

- Section 1: for Dose 1
  - a) The Treatment administration questionnaire for Dose 1
  - b) The Treatment Acceptability Questionnaire after Dose 1
  - c) Symptoms Scale
- Section 2: for Dose 2
  - a) The Treatment administration questionnaire for Dose 2
  - b) The Treatment Acceptability Questionnaire after Dose 2
  - c) Symptoms Scale
- Section 3: after preparation intake but before colonoscopy

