### Klean-prep®:

Klean-prep® is provided as powder for oral solution in sachets containing a whitish powder which, when dissolved in water, gives a clear, colourless solution for oral administration. Each sachet contains: macrogol 3350: 59.000 g, anhydrous sodium sulphate: 5.685 g, sodium bicarbonate: 1.685 g, sodium chloride: 1.465 g, potassium chloride: 0.7425 g. Klean-prep® should be stored at the recommended temperature (not above 25°C). A total of 69 g of the product (powder for oral solution) is included in one sachet. Each treatment pack is composed of 4 sachets.

A more detailed description of administration procedures is given in Section 6.1.2.

In this single-blinded study, to ensure an unbiased evaluation of the study preparations, the colonoscopist will not be allowed to perform any study drug related activities (randomisation, drug dispensing, return and accountability, acceptability, tolerability and review of subject's leaflet/questionnaires). Any failure to maintain blinding of the treatment for the colonoscopist will be documented as a protocol violation. Subjects and caregivers will be instructed not to discuss their study preparation with the colonoscopist or any staff member other than with the study nurse who will collect the questionnaires.

A rescue treatment (normal saline enema, 1000 mL) may be administered only if clear discharge has not been obtained 1 hour prior to procedure. This rescue medication will be given repeatedly until clear discharge is obtained. Sodium phosphate enemas are not to be used. The need for a rescue treatment will be recorded in the eCRF.

The investigational medicinal product (IMP) Eziclen®/Izinova® and Klean-PREP® will be packaged and released by the Beaufour Ipsen Industrie, CMC-SC and delivered to the investigational sites or deposited in an Interim Storage Facility. A sufficient quantity of Eziclen®/Izinova® and Klean-Prep® will be supplied as well as an acknowledgement of receipt form. The Sponsor's representative will receive a Certificate of Analysis for the IMP batches of the study, Material Safety Data Sheet for both active and comparative treatment, Packaging order and the Certificate of Compliance which reflects the product's release statement and will provide them to the sites according to local requirements.

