# 3.8 Maintenance of Randomisation and Blinding

This study being investigator-blinded, the eCRF will provide two user profiles: one profile (e.g. pharmacist) which will be able to see the treatment arm and another one for the investigator for whom this information will be hidden. The tear-off of pack labels will indicate the treatment number to be entered in the eCRF, it will be similar for Eziclen®/Izinova® and Klean-Prep®. However, the appearance and contents of packs being different, to maintain the blinding for the investigator, the randomisation/dispensation of assigned treatment will be done by a pharmacist/nurse in charge of this activity. This person will be fully trained about the importance of his role in maintaining the blind for the investigator.

Two sets of individual sealed code break envelopes (refer to List B) will be prepared by the sponsor's randomisation manager to enable emergency code break procedures for individual subjects without compromising the blind of the study. One set will be provided to the investigational site and one set will be provided to the Global Patient Safety of the sponsor. The sending of code-break envelopes "investigator" will have to be coordinated with the sending of associated treatment kits.

Code break envelopes will only be opened in cases of medical emergency when treatment is dependent on knowledge of the IMP received.

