# 6.3 Procedures for Monitoring Subject Compliance

In order to maintain the investigator-blind, administration compliance will be assessed by dedicated personnel based on measurement of unused preparation and fluid intake recorded by the subject/caregiver on the subject's leaflet. Data collected on the subject's leaflet will be reviewed outside of the colonoscopist's presence and will not be made available to the colonoscopist.

Data will be entered in the eCRF by unblinded personnel as single data entry (one person enters the data in the eCRF). Data verification will be performed by study monitor during on site visits.

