# 7.3.2.2 Treatment/Compliance

The treatment questionnaire will be completed by the caregiver or subject after the subject completes each dose of preparation. The subject/caregiver will provide information about treatment preparation, residual volumes of preparation (volumes not taken by the subject) and start and stop times of intake. For the Eziclen®/Izinova® treatment only, information about the residual volume of water will be reported.

PAGE 48/103

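### Protocol 14.2.2 allows the arm-identifying leaflet to reach the principal investigator and the medical file, in conflict with the investigator blind in 3.8

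*Protocol*

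**What the plan says.** Protocol 14.2.2 provides two leaflets: "Either the Eziclen®/Izinova® leaflet" or the Klean-Prep one. The contents differ as well. Under 7.3.2.2, "For the Eziclen®/Izinova® treatment only, information about the residual volume of water will be reported". The same section 14.2.2 states that the leaflet, a single paper copy, is "provided to the principal investigator/study nurse who will file it in the subject's medical/study file".

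Under 14.2.1, unblinded site staff enter the leaflet data, but "The principal investigator will ensure that these data are complete and accurately represent the study subject information" by signing the eCRF. Section 14.1 also asks the investigator to sign each case report book for all of its data.

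On blinding, 3.8 sets up one eCRF profile that can see the arm and "another one for the investigator for whom this information will be hidden". Section 3.4 keeps the colonoscopist out of drug-related activities, a list that ends with "acceptability, tolerability and review of subject's leaflet/questionnaires". Section 6.3 adds that leaflet data "will be reviewed outside of the colonoscopist's presence and will not be made available to the colonoscopist".

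**The concern.** The trial is single-blind. Subjects and caregivers know the product, so the protection against assessment bias rests on the people at the site who make judgements. Section 14.2.2 names one of them, the principal investigator, as a permitted recipient of a document that identifies the arm. It also names the medical file as a permitted place to keep it. No section says that the principal investigator is unblinded, and none restricts access to the file. With around 25 centres planned, a site could follow 14.2.2 exactly and still unblind its investigator.

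At stake are judgements that cannot be checked afterwards: whether an adverse event is related to the preparation and, for a few subjects, whether the preparation counts as a failure.

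**Working it through.** No figure in the plan depends on this point, so the check is mainly a comparison of sections.

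**1. Does the leaflet identify the arm?** Yes, by product name (14.2.2) and by content, since residual water is recorded in one arm only (7.3.2.2).

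**2. Who handles it?**

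| Step | Role named | Section |
|---|---|---|
| Dispensing | Study nurse | 5.1 (Table 4), 5.2.2 |
| Collection at Visit 2 | Study nurse | 5.1 (Table 4) |
| Data entry | Unblinded personnel | 6.3, 14.1, 14.2.1 |
| Receipt and filing | Principal investigator or study nurse; medical or study file | 14.2.2 |
| Attestation | Principal investigator | 14.2.1; see also 14.1 |

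The first three steps fit the blind. The last two are the outliers.

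**3. Which judgements does the investigator make?**
- Causality of every adverse event (8.1.3). Leaflet symptom ratings of 2 to 5 must be reported as adverse events (8.6), so part of what the investigator must assess originates on the arm-identifying paper. Comparing safety and tolerability is a secondary objective (2.2.2).
- One failure category in the primary endpoint. A subject without a colonoscopy is a failure if the reason was the investigator's view of the cleansing or a preparation-related adverse event (Protocol 10.4.5; SAP 3.2.1.1).

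**4. Does the exposure reach the cleansing grade?** The colonoscopist gives the grade on completing the examination (3.2.1). Section 5.2.3 says only that a physician performs the colonoscopy, and nothing bars the investigator from that role. Sections 3.2.2.2 and 8.5 refer to lesions that the investigator suspects were caused by lavage, which suggests that the two roles may overlap. The last part of the leaflet is completed before colonoscopy (14.2.2), so the paper can exist before the grade. The route is therefore conditional: it needs one person in both roles, or a medical file that the colonoscopist can open.

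**5. Are the planned numbers affected?** The stated sample size reproduces. With 85% success in both arms, a 15-point margin, one-sided alpha 0.025 and 90% power, n = 2 × 0.85 × 0.15 × (1.960 + 1.282)² / 0.15² = 119.08, so 120 per arm. Then 120 / 0.96 = 125 per arm. Power at 120 per arm is 90.2%. Neither the concern nor the fix changes these figures.

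**6. How sensitive is the test to biased outcome assessment?** This is an illustration with assumed shifts, not an estimate. Take a true difference of −15 points (85% versus 70%, 120 per arm) and a net shift b towards the test arm. The one-sided type I error is Φ(b/SE − 1.960), with SE computed at 85% and 70% + b.

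| Assumed shift b (points) | Type I error |
|---|---|
| 0 | 2.5% |
| 1 | 3.8% |
| 2 | 5.7% |
| 3 | 8.3% |
| 5 | 16.3% |

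Nothing in the documents says that any of these shifts would occur.

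**The case against.** The strongest reply is that 14.2.2 offers alternatives. If the study nurse files the leaflet in the study file, the section is followed to the letter and the blind holds. The schedule and the data-entry rules point to that route, and 3.4 tells subjects to discuss the preparation only with the nurse. This stands: the text permits a breach and does not require one. It does not remove the problem, because the other alternative remains open to every site.

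A reader might infer that the primary cleansing grade is unblinded as well. The documents do not support that. Sections 3.4 and 6.3 keep the colonoscopist from the leaflet and its data, and 3.4 makes any failure of that blind a protocol violation. The bar attaches to the role, so an investigator who performs the colonoscopy is also covered by it. What remains is that 14.2.2 makes no exception for such an investigator, and that 6.3 protects the colonoscopist in the name of the investigator blind without separating the two roles. That the colonoscopist can read the medical file is an assumption, since file access is not described.

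It is also fair to say that an electronic signature does not prove that the signatory saw the arm. The investigator's eCRF profile hides it, and no section gives the timing of the signature. But 14.2.1 asks the principal investigator to ensure that leaflet data are complete and accurate, and does not say how that can be done from a profile that hides the arm.

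**Conclusion.** Sections 14.2.2 and 14.2.1 conflict with the investigator blind in 3.8 and sit badly with the colonoscopist safeguards in 3.4 and 6.3. Where a site uses the investigator route, the direct exposure is adverse event causality and the no-colonoscopy failure category. The cleansing grade is exposed only under the two conditions in step 4 of the working.

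The size of any bias cannot be estimated. A reader might try to multiply an assumed share of unblinded subjects by an assumed share regraded, but the documents give neither figure. Such a product also ignores direction: regrading biases the difference only if it systematically favours one arm. The type I error figures above show why the blind is worth protecting and nothing more.

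The conclusion assumes that no charter, manual or site instruction outside these documents already restricts the leaflet. It is worth correcting because the remedy is cheap and the affected judgements are subjective.

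**What to change.** - **14.2.2:** name only the unblinded nurse or pharmacist to receive and file the leaflet. Keep it in a restricted file, closed to the investigator and the colonoscopist until the codes are released.
- **14.2.1 and 14.1:** have the unblinded designee verify and sign the leaflet and study-drug pages. Before code release, limit the investigator's signature to pages visible in the blinded profile. A later countersignature would respect the investigator's responsibility for all site data under 12.3.
- **8.6 and 8.1.3:** pass the leaflet symptom ratings to the investigator in a product-neutral form, so that adverse events and their causality can be assessed blind. Without this step, closing the leaflet to the investigator would leave adverse event reporting undefined.

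The cost is protocol wording, changed eCRF signature rights and a second file at each site. Unblinded staff and the two-profile eCRF already exist. Sample size, alpha and the planned analyses stay as they are.
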